## 6.6 Unscheduled Angiogram

If a subject undergoes an angiogram that is not required as part of this study protocol, it is considered an unscheduled angiogram. If a subject has an unscheduled angiogram, it should be performed using the same orthogonal views as used during the index embolization procedure, and according to the study Core Lab Manual. The angiogram images should be uploaded or sent to the study Image Management System.

## 6.7 Summary of Follow-up Schedule and Time Windows

**Table 5: Follow-up visits: Schedule & Time Windows**

Follow-up Visit	Time Window (days)	Timeframe
30 days*	16 - 44	days after index procedure
6 month	92 - 212	days after index procedure
12 month	320 - 410	days after index procedure
18 month*	457 - 592	days after index procedure
24 month	685 - 775	days after index procedure
Stroke or suspected stroke visit	16 - 44	days after stroke or suspected stroke**

\* May be a Telephone Visit

\*\* If a subject experiences a stroke, or if there is any suspicion of a stroke, the subject needs to have an MRI completed within a **time** window of 24 hours **after** symptom(s) onset. In the event, that the subject experienced a stroke but the investigator did not learn about the stroke at the time it occurred, and thus an MRI was not done within 24 hours of the stroke, then site must obtain an MRI immediately upon learning of the stroke, as well perform the modified Rankin Score (mRS) assessment and the National Institute of Health Stroke Scale (NIHSS).

All follow-up assessments will be performed at the specified times indicated unless a subject suffers an adverse event that prevents evaluation. Under these

circumstances, only clinically indicated assessments will be performed at the discretion of the attending physician.

## 7 CORE LABORATORY

An independent core laboratory will perform the quantitative angiographic measurements for the primary and secondary effectiveness endpoints and the 24 month follow up using the Raymond scale assessment. These measurements will be performed by an independent reader.

All subjects are to have procedural angiograms (at pre-treatment, intra-procedure, and immediate post-treatment), as well as 6 and 12 and (if applicable) 24 month angiograms. The angiograms need to be performed according to the study Core Lab Manual. Standard quantitative angiography (QCA) acquisition procedures will be followed for QCA analysis. All angiographies must provide angiograms that are suitable for quantitative analysis, based on optimal orthogonal catheter arteriographic projections. Refer to the study Core Laboratory Manual for further angiographic methods and requirements.

## 8 CONCOMITANT MEDICATIONS

The following concomitant medications are a requirement of this protocol. Regardless of the therapy administered, the concomitant medication(s) will be documented on the eCRF.

### 8.1 Pre-procedure Medications

- Aspirin (ASA): At least 81 mg/day for a minimum of 7 days prior to the procedure
- P2Y12 Platelet Inhibitor: Daily for a minimum of 7 days prior to the procedure

**Note:** Confirmation of correct antiplatelet therapy prior to the procedure must be documented; If not available, the procedure should be delayed.

### 8.2 Intra-procedure

- General anesthesia is required for the procedure.
- Heparin: A bolus of intravenous heparin will be given that is weight adjusted to maintain the activated clotting time (ACT) near 250-300 seconds throughout the procedure. If a GP IIb-IIIa Inhibitor (Reopro or Integrilin) is given during the procedure, then the ACT should be maintained at less than 220 to minimize the risk of bleeding. GP IIb-IIIa Inhibitors should not be given if the subject has a recent history (less than 30 days) of hemorrhage. It is required that the ACT be checked during the procedure at intervals of no longer than 60 minutes, as well as at the

end of the procedure to verify conformity with this requirement. It is recommended to discontinue heparin at the end of the procedure and the arterial sheath removed after the ACT has returned to < 140 seconds.

The use of vascular closure devices is recommended, but sheath removal on the day following the procedure is acceptable.

### **8.3 Post-procedure**

The following post-procedure medications are required per this protocol.

- ASA (at least 81 mg/day) must be continued for a minimum of 12 months.
- P2Y12 Platelet Inhibitor must be taken daily for a minimum of 3 months.

## **9 STATISTICAL METHODS**

The following sections provide a general description of the statistical plan for the analysis of study data. A separate Statistical Analysis Plan (SAP) document that provides greater detail on data derivations and the analyses to be performed will be developed prior to the planned interim analysis. The SAP will reflect the protocol and any amendments that have been implemented at the time the SAP is finalized. Any deviations from the final SAP will be noted in the final clinical summary report.

### **9.1 Study Design**

This is a prospective, multi-center, single arm, clinical study to evaluate the safety and effectiveness of the ENTERPRISE stent when used in conjunction with endovascular coil embolization in the treatment of unruptured wide-neck, intracranial, saccular anterior circulation aneurysms ( $\leq 10$  mm) arising from a parent vessel with a diameter of  $\geq 2.5$  mm and  $\leq 4$  mm. A group sequential design will be utilized in which one primary endpoint interim analysis will be conducted after  $N=160$  subjects have been enrolled and followed through 6 months post-procedure. Enrollment will pause after these 160 subjects have been enrolled and will not resume until after the interim analysis has been conducted. The purpose of the interim analysis will be to determine whether or not to terminate the trial early for futility or tentative success. If the stopping rule is met for the trial to stop early for tentative success, a final confirmatory analysis will be conducted when all subjects have reached 12 months post-procedure. If the trial is not terminated early for futility or tentative success, then enrollment will continue up to a full enrollment sample size of  $N=320$ . After all 320 subjects have reached 12 months post-procedure, a final analysis will be conducted.

### **9.2 Treatment Assignment**

This is a single arm study; all subjects will be treated with the CODMAN ENTERPRISE device.

### **9.3 Levels of Significance**

A 2-sided alpha of 0.05 will be used for statistical testing and confidence intervals unless otherwise noted. There will be no adjustment to p-values or alpha levels for testing primary safety, secondary effectiveness, or secondary safety endpoints.

A primary efficacy endpoint interim analysis will be conducted to determine whether or not to stop the trial early for futility or tentative success. This analysis will be based solely on the primary efficacy endpoint, and will be conducted after N=160 subjects have been enrolled and have reached 6 months post-procedure. In this interim analysis, the two-sided unadjusted p-value threshold for stopping the trial early for success will be 0.031. If the stopping rule is met for the trial to stop early for tentative success, a final confirmatory analysis will be conducted when all subjects have reached 12 months post-procedure; a p-value threshold of 0.031 will be used for this final confirmatory analysis. If this early stopping rule is not met, then enrollment will commence until the total sample of N=320 subjects have been enrolled (including the original N=160). The final endpoint analysis with all be conducted with a 2-sided p-value threshold of 0.031 for determining study success. These p-value thresholds have been established in order to maintain an overall 2-side alpha (probability of a Type 1 error) below 0.05 for the primary endpoint.

### **9.4 Interval Windows**

The baseline/screening evaluation is to be done between 14 days prior to the procedure and the day of the index procedure, which is considered to be day 0. The immediate pre-procedure evaluation (which includes angiographic assessment) and immediate post-procedure assessment will be considered within window if they occur within 12 hours (before and after, respectively) of the start of the index procedure (groin stick). The assessment at hospital discharge will occur between 12 and 36 hours after the start of the index procedure. The 30 day, 6 month, 12 month, 18 month and 24 month assessments will occur in the time intervals (days) indicated in the following table:

Study Interval Windows [days or hours, as indicated]	
Baseline/Screening	-14 to 0
Immediate Pre-Procedure	Within 12 hours prior to procedure
Index Procedure	Day 0
Immediate Post-Procedure	Within 12 hours after procedure
Hospital Discharge	12 to 36 hours after procedure
30 Days	16 to 44 days after procedure
6 Months	92 to 212 days after procedure

12 Months	320 to 410 days after procedure
18 Months	457 to 592 days after procedure
24 Months	685 to 775 days after procedure

## 9.5 Handling of Missing Data

Primary effectiveness and primary safety endpoint analyses will be conducted on the modified intent-to-treat (MITT) population, where subjects with missing data at the time of endpoint analysis will be imputed as last observation carried forward (LOCF); see Section 9.8 for analysis set definitions. Note that the immediate post-procedure evaluation will be utilized in this LOCF methodology if this is the last observation on file. MITT subjects who receive the device but in whom there is no post-procedure data will be treated as failures for the purpose of the primary effectiveness endpoint analysis; these subjects will be excluded from all other endpoint analyses. Subjects who do not receive the device because of treatment failure due to reasons associated with the device will also be treated as failures for the primary effectiveness endpoint analysis; these subjects will be excluded from all other endpoint analyses. MITT subjects who do not receive the device because of an intra-operative surgeon decision based on patient anatomy (e.g. vessel tortuosity) will be treated as missing (and not as failures) in all endpoint analyses, including the primary effectiveness and primary safety endpoint analysis.

All subjects who have died prior to an evaluation will have a mRS score of 6 imputed for that time point for analysis purposes.

All other analyses based upon MITT or PP population data will be based upon actual data, with no data imputation.

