More recent studies are showing that refinement of microsurgical technique is leading to safer, more efficacious treatment of UIAs. One study followed a series of 450 aneurysms treated with surgical clipping by one neurosurgeon immediately upon completion of neurosurgery training. With 6-month morbidity and mortality rates of 1.06% and 0.27%, respectively, it is clear that, given proper mentorship and resources prevailing neurosurgeons can achieve acceptable results when treating UIAs surgically (Nussbaum et al., 2007).

Since its conception and implementation about two decades ago (Guglielmi et al., 1991a; Guglielmi et al., 1991b), endovascular coil embolization has become a primary treatment in the management of unruptured intracranial saccular aneurysms. In many institutions worldwide, endovascular coiling has become the preferred treatment for unruptured intracranial saccular

aneurysms for which intervention is indicated (Moyle and Patel, 2010). To confirm the notion that endovascular procedures provide a safe alternative for treating unruptured intracranial saccular aneurysms, many studies have investigated the morbidity and mortality rates of patients who underwent endovascular coiling. As part of the prospective branch of the ISUIA, 451 patients were chosen to undergo endovascular coiling. Among these patients, there was a 1-year surgery-related mortality rate of 3.1% and a 1-year morbidity rate of 9.5% (Wiebers et al., 2003). A year later, Lanterna et al. (2004) analyzed thirty studies of endovascular coiling, published between 1990 and 2002, and revealed case-fatality and permanent morbidity rates of 0.6% and 7.0%, respectively. To appreciate the effect of advancing technology and technical refinement, the investigators divided the publications by midyear of the study and found that studies before 1995 reported a morbidity rate of 8.6%, while the morbidity rate of studies after 1995 had dropped to 4.5% (Lanterna et al., 2004). Another more recent meta-analysis performed by Naggara et al. (2010) looked at similar studies performed in 17 different countries from 2003 to 2008 and found unfavorable outcomes occurred at a rate of 4.8%. Ultimately, these data do seem to indicate that endovascular coiling provides a safe alternative to clipping by imparting lower complication rates upon patients.

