The technical success measures were also assessed using the angiographic core lab. Successful intracranial device placement (defined as stable CODMAN ENTERPRISE placement with complete coverage of the aneurysm neck and parent artery patency) was achieved in 85.7% of the cases. Satisfactory coil mass position (defined as CODMAN ENTERPRISE maintains coil position within the sac with parent artery patency as defined angiographically) was 83.5% immediately post-procedure and 83.3% at six months. Complete aneurysm occlusion was achieved in 20.2% of cases immediately post-procedure and in 58.2% of the subjects with 6 months follow-up.

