
## 3.2 Study Endpoints

### 3.2.1 Primary Effectiveness Endpoint

- The primary effectiveness endpoint is the Rate of Complete Aneurysm Occlusion (RCAO) at 12 months post-procedure according to the Raymond Scale as assessed by the Independent Core Laboratory.

Complete aneurysm occlusion is defined as an aneurysm in which a score of 1 (complete obliteration) is achieved on the Raymond Scale at the relevant post-procedure angiogram, without additional procedures for treatment of the aneurysm since the index procedure. Subjects who are retreated (retreatment includes staged procedures) prior to the 12 month post-procedure follow-up visit will be considered not to have achieved complete aneurysm occlusion for the purpose of the primary endpoint analysis.

The primary endpoint analysis will be to demonstrate that the RCAO is significantly greater than a performance goal (PG) of 35%. The primary endpoint null and alternative hypotheses are:

Null hypothesis  $H_0$ :  $\text{RCAO} \leq 35\%$

Alternative hypothesis  $H_A$ :  $\text{RCAO} > 35\%$

This analysis will be conducted on the modified intent-to-treat (MITT) population of subjects (subjects who are found to be eligible for treatment with ENTEPRISE at the time of the pre-procedure angiographic assessment, and in whom treatment is attempted). A supportive analysis will be conducted on the PP population.

**Note:** The study will be deemed to be a success if this primary efficacy endpoint null hypothesis (on the MITT population with data from all sites combined) is rejected in favor of the alternative hypothesis.

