#### **9.11 Plans for Interim Analysis**

This study is a group sequential design in which one primary endpoint interim analysis will be conducted after N=160 subjects have been enrolled and followed through 6 months post-procedure. The purpose of the interim analysis will be to determine whether or not to terminate the trial early for futility or tentative success. This analysis will be a test of the primary efficacy endpoint only, and will be conducted after N=160 subjects have been enrolled and have reached 6 months post-procedure. LOCF imputation methodology will be utilized for subjects who do not have 12 month post-procedure data, so that 6 month primary endpoint data will serve as a surrogate for 12 month data for subjects who have not yet reached 12 months post-procedure.

The trial will stop early and will be deemed to be tentatively successful if the two-sided unadjusted p-value for this primary efficacy endpoint analysis is below 0.031. If the stopping rule is met for the trial to stop early for tentative success, a final confirmatory analysis will be conducted when all subjects have reached 12 months post-procedure; a p-value threshold of 0.031 will be used for this final confirmatory analysis. The trial will stop early for futility and it will be decided that the study would not have been successful even if the study would have continued to an enrollment of N=320 if the two-sided unadjusted p-value for this primary efficacy endpoint analysis is above 0.358. If neither of these criteria are met, or if the confirmatory analysis for early success is not satisfied, then enrollment will commence until the total sample of N=320 subjects have been enrolled (including the original N=160), and the final endpoint analysis will be conducted after all 320 subjects have reached 12 months post-procedure. In the case that the study continues to a full enrollment of N=320, the study will be deemed to be a success if the two-sided unadjusted p-value for the final primary efficacy endpoint analysis is below 0.031.

If a decision is made to stop the trial early for either futility or tentative success, follow-up will continue through 12 months post-procedure for all enrolled subjects. Further details of this planned interim analysis are provided in sections 9.1 (Study Design), 9.3 (Levels of Significance), 9.7 (Hypotheses), and 9.9 (Sample Size Justification).

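### Protocol 9.5 carries the last Raymond reading forward with no exception for death, so a subject who dies after a class 1 reading counts as a 12-month occlusion success

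*Protocol*

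**What the plan says.** - **Carry-forward rule.** Protocol 9.5 sets the missing-data rule for primary effectiveness in the MITT population: "subjects with missing data at the time of endpoint analysis will be imputed as last observation carried forward (LOCF". The Overview (Sample Size Determination) and sections 3.1 and 9.10.5 repeat it. The earliest reading that can be carried is the one at the end of the procedure: "Note that the immediate post-procedure evaluation will be utilized in this LOCF methodology if this is the last observation on file".
- **Exceptions in 9.5.** An implanted subject with no post-procedure data is a failure. So is a subject not implanted for a device-related reason. A subject not implanted because of anatomy is treated as missing.
- **Retreatment.** Protocol 3.2.1, repeated in 9.6: "Subjects who are retreated (retreatment includes staged procedures) prior to the 12 month post-procedure follow-up visit will be considered not to have achieved complete" occlusion.
- **Death.** The only rule in 9.5 concerns the Rankin scale: "All subjects who have died prior to an evaluation will have a mRS score of 6 imputed for that time point for analysis purposes". Otherwise death counts as part of the first primary safety endpoint (9.6, 9.7).
- **Interim.** Protocol 9.11: "LOCF imputation methodology will be utilized for subjects who do not have 12 month post-procedure data".
- **SAP for the terminated study.** Section 10.4.1.1 leaves out subjects with no 12-month Raymond score. Section 10.6 imputes nothing unless stated otherwise. Sections 6 and 10.4 drop the hypothesis tests and 10.5 drops the interim analysis. Section 10.4.2.2 keeps the Rankin score of 6 for deaths, but no section gives a rule for deaths in RCAO.

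**The concern.** RCAO is defined at 12 months, and a subject who has died has no 12-month occlusion state. Because 9.5 exempts some subjects from LOCF but not those who die, a death is ordinary missing data and the last reading stands.

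The resulting order is hard to defend. A living subject retreated for rupture or bleeding is a failure, but one who dies of that rupture before retreatment is a success if the last reading was class 1. A subject who dies before any post-procedure reading is a failure; one who dies after a class 1 reading is a success. The Protocol treats death as informative for the Rankin scale, yet gives no rule for the one endpoint that defines study success.

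At stake under the Protocol are the interim, confirmatory and final tests of RCAO against 35%. Under the SAP, what is at stake is only who is in the denominator of a descriptive rate.

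**Working it through.** **1. Reproduce the design figures.** Inputs from the Protocol: goal 35%, success at two-sided p < 0.031, 150 evaluable subjects at the interim and 300 at the final analysis. The test is z = (x/n − 0.35) / √(0.35 × 0.65 / n).

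- n = 150: 66/150 gives z = 2.31, p = 0.0208 (success); 65/150 gives p = 0.0324 (not).
- n = 300: 123/300 gives z = 2.18, p = 0.0293 (success); 122/300 gives p = 0.0396 (not).

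With X1 and X2 independent Binomial(150, p), overall success = P(X1 ≥ 66) + Σ over i < 66 of P(X1 = i) × P(X2 ≥ 123 − i). Futility is not enforced, and interim success is counted as success. This gives 2.70% at 35% (table under Protocol 9.9: 2.7%), 87.6% at 44% (87.7%) and 98.6% at 47% (98.6%). Interim success at 47% is 79.3% (79.3%). The Protocol's figures stand.

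**2. Size of the credit.** Added RCAO = mortality × share of deaths whose last reading is class 1. The documents give neither figure for this trial, so both are assumptions taken from the Protocol's background.

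- Mortality (all in 1.1.3): 0.6% across thirty coiling studies; 0.9% for standard coiling and 1.4% for balloon remodelling in unruptured aneurysms; 2.0% in a stent-coiling registry that included ruptured aneurysms; and, for a coiling cohort, "there was a 1-year surgery-related mortality rate of 3.1% and a 1-year morbidity rate of 9.5"%.
- Class 1 share (1.3.4): "Complete aneurysm occlusion was achieved in 20.2% of cases immediately post-procedure and in 58.2% of the subjects with 6 months follow-up".

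**3. Effect on the test.** Suppose the rate with deaths as failures is exactly 35%. Putting 35% plus the added points into the formula in step 1 gives:

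| Mortality × class 1 share | Added points | Chance of declaring success |
|---|---|---|
| none | 0 | 2.7% |
| 0.6% × 20.2% | 0.12 | 3.0% |
| 1.4% × 58.2% | 0.81 | 4.9% |
| 2.0% × 20.2% | 0.40 | 3.7% |
| 3.1% × 20.2% | 0.63 | 4.3% |
| 3.1% × 58.2% | 1.80 | 9.4% |

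Per 300 subjects, 0.12 to 1.80 points is 0.4 to 5.4 credited deaths. At either critical count in step 1, one reclassified death changes the result.

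The last row needs the highest mortality and every death to follow a 6-month angiogram. Earlier deaths have only the acute reading, for which the share is 20.2%.

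**4. The SAP's rule.** Take 300 subjects with 132 counted successes, including 3 of 6 deaths.

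- LOCF: 132/300 = 44.0%.
- Exclusion (SAP): 129/294 = 43.9%.
- Death as failure: 129/300 = 43.0%.

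Exclusion removes the credited success but does not count the death as a failure. A subject with a reading in the SAP's 12-month window (Day 270 to 450) keeps that reading.

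**The case against.** The strongest reply is that the SAP has overtaken the rule. The study stopped for low enrolment, no test will be run, and LOCF is gone. A reader might infer that the final reported RCAO will be inflated by deaths scored as successes, or that the chances in the table apply to it. The documents support neither. What remains is that the SAP takes these deaths out of the denominator.

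Second, mortality should be low. The trial excludes ruptured aneurysms, caps age at 70 and aneurysm size at 10 mm, and excludes patients without a 5-year life expectancy. This stands, and it is why the lower part of the range is the more plausible. A reader might take 1.8 points and 9.4% as the expected effect, but they are the corner of the range.

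Third, RCAO is an anatomical reading, and death is already counted in a primary safety endpoint with its own 25% goal. Scoring death as an occlusion failure is therefore a choice of estimand. That is fair, but the Protocol already scores retreatment and absent data as failures, and leaving death to LOCF is not a stated choice.

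Fourth, a reader might infer that LOCF always favours the device. That holds only against death as failure. Against exclusion, carrying an acute reading (20.2% class 1) for an early death would usually lower RCAO, since occlusion rises to 58.2% by 6 months.

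Nor is the Protocol's Type 1 error figure wrong. It reproduces; the higher figures take death as failure to be the true null.

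**Conclusion.** The point holds as an omission in the Protocol's rule. It follows from the absence of a death exception, not from any sentence about deaths. It applies only when the last reading on file is class 1 and the aneurysm was not retreated; a death with no post-procedure data is already a failure.

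Relative to death as failure, the rule can only raise RCAO: by about 0.1 to 1.8 points over the assumed ranges, most plausibly under 1 point. The matching chance of a false declaration at 35% is about 3.0% to 4.9% for mortality of 0.6% to 1.4%, which is still below 5%, and 9.4% only at the extreme. These figures concern the Protocol's planned interim, confirmatory and final tests, none of which the SAP runs.

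For the current descriptive analysis the point is minor: subjects who die without an in-window 12-month reading leave the RCAO denominator when they should count as not occluded.

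**What to change.** - **Protocol 9.5, 9.6 and 9.11.** State that a subject who dies before the 12-month angiographic assessment counts as not having achieved complete occlusion, and that LOCF does not apply to that subject. Apply this at the interim, confirmatory and final analyses.
- **SAP 10.4.1.1.** Keep such deaths in the denominator as not achieving complete occlusion. List every death with its last Raymond class, so that a reader can see the effect of either rule.

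The cost is one sentence per section, a line of code and a short listing. No extra subjects, visits or procedures are needed. The downside is a slightly less favourable RCAO.
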